A Third-Wave Intervention for Internalized Weight Bias Combined With a Weight Loss
Program Using Video Conferencing Software

NCT Number: Not yet assigned

Document Date: 08/11/2022

Study Protocol & Statistical Analysis

Participants

Participants will be recruited for the study using an email Listerv announcement to individuals throughout the university and associated community. Participants must indicate that they are interested in weight loss and are interested in participation for the entire program before being accepted. Other inclusion and exclusion criteria require that participants be 18 or older, at a BMI of 25 kg/m² or greater, and are not pregnant or planning to become pregnant. Based on average scores for Durso and Latner's (2008) Weight Bias Internalization Scale and in staying consistent with Pearl, Wadden, Bach, Gruber, et al.'s (2020) research, individuals will also be screened for higher-than-average levels of IWBI, with a cutoff of 4 or higher. Individuals who have already successfully lost more than 5% of their body weight within the past six months will be excluded. Individuals with current use of medication prescribed for weight loss (such as orlistat, sibutramine, or rimonabant) will also be excluded. In addition, participants must have access to internet, along with a web camera and sound, and be able to use video conferencing software and attend weekly online groups. They will also need access to a reliable scale to weigh themselves weekly.

According to an a priori analyses run using G*Power, a sample size of 40 will be required to detect a medium effect size for a 2 x 2 repeated measures analysis of variance (ANOVA; Faul et al., 2007). A medium effect size was selected for a couple of reasons. First, this is consistent with previous literature, as Pearl, Wadden, Bach, Gruber, et al. (2020) also structured their methodology on detecting a medium effect size. Second, this study aims to examine the efficacy of an intervention. However, an intervention that produces only a small effect may be

less clinically meaningful than an intervention that produces a medium or large effect size. Due to attrition concerns, the sample size for the proposed study will be 70, with 35 individuals per group.

Interventions

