Diabetes Prevention Program (DPP). All participants will participate in a behavioral weight loss program (BWLP). The program will be a 12-week adapted version of the DPP. As previously mentioned, the DPP is a widely used, evidence-based program that has been found to be applicable to individuals of varied backgrounds, and has overall become the gold-standard for behavioral weight loss programs (DPP Research Group, 2002a). Several studies have found the DPP to produce statistically significant weight loss when delivered through an online format (Azar et al., 2015; Carels et al., 2021; Vadheim et al., 2010). See Appendix A for a list of session topics.

Third-Wave Based Internalized Weight Bias Intervention. ACT-based programs and self-compassion have shown promise throughout research for lowering IWB (Berman et al., 2016; Levin et al., 2018; Lillis et al., 2009; Palmeira, Cunha, & Pinto-Gouveia, 2017; Palmeira, Pinto-Gouveia, & Cunha, 2017; Forbes et al., 2020). Therefore, using techniques from prior ACT- and self-compassion based programs, a weight bias reduction intervention will be administered. Session topics will include psychoeducation, observing myths and stereotypes, and using internal and external coping for weight bias, and these topics will be viewed through a self-compassionate and ACT-based or DBT-based lens (for example, participants may defuse from internal critical thoughts rather than challenge them). Sessions will also cover acceptance, cognitive defusion, mindfulness, committed action, and self-compassion. Participants will be

asked to keep a self-compassion journal to practice third-wave and self-compassion skills and techniques. See Appendix B for a list of session topics.

Procedure

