Participants will complete an initial digital screener to determine eligibility. Once it is determined that eligibility criteria are met, participants will be randomly assigned into one of two groups. Both groups will initially receive a weight loss intervention using the DPP through twelve weekly, hour long virtual sessions as led by clinical health psychology doctoral students with previous weight loss intervention experience. In addition, group leaders will look for opportunities to incorporate weight bias reduction strategies throughout the DPP when possible. However, only one group will be administered a third-wave, ACT and self-compassion-based IWB intervention for 30 minutes after the 60 minute weight loss intervention. Both groups will receive information on how to monitor eating behavior through MyFitnessPal, exercise through MyFitnessPal or smart devices, and will be encouraged to weigh themselves weekly or more. The IWB program will begin after the first four sessions of the DPP so that participants can spend the first month adjusting to weight loss treatment.

Measures

All measures will be completed at baseline and post-intervention online. Demographic information will also be collected at baseline. In addition, participant weight and height will be collected in person, using a digital scale and stadiometer, at baseline and post-intervention. If participants drop out of the study, they will be asked to complete the post-intervention surveys and attend a weigh-in, if possible.

Demographics. All participants will complete demographic questions assessing age, sex, gender, race/ethnicity, sexual orientation, income, education, and self-reported height and weight. Participants will also be asked about their desire for weight loss.

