situation (i.e., “I am satisfied with the quality of the therapy I received” will be adapted to “I am satisfied with the quality of the telehealth weight loss treatment I received”). Similarly, questions about the therapist will be changed to “weight loss coach.” The STTS-R has been shown to have reliability for both the scale as a whole ($\alpha = .90$) and the subscales Satisfaction with Therapy ($\alpha = .91$) and Client Evaluation of Therapist ($\alpha = .80$).

Statistical Analysis Plan

All analyses will be conducted in SPSS 28 (IBM Corp., 2021). Data will be cleaned and screened before proceeding with analysis. Descriptive statistics will first be examined for the overall sample. Then, demographics among each group will be examined. Preliminary analyses will be run to ensure that there were no significant group differences in terms of basic demographics. Continuous variables will be examined using t-tests or ANOVA (for example, BMI) while dichotomous and categorical variables will be examined using chi-square (i.e., race/ethnicity). While it is hoped that randomization will provide even group characteristics, any potential group differences will be included as a covariate in analyses. Also, upon study conclusion, group differences will also be examined in terms of attrition and number of sessions attended to check whether treatment impacted these factors.

Hypothesis One and Hypothesis Two. A series of 2×2 (time x group) repeated measures ANOVA will be utilized to examine whether the BWLP only and Third-Wave + BWLP groups were successful with lowering weight, IWB, and weight bias and increasing healthy eating and physical activity and whether there are differences between the BWLP only group with the Third-Wave + BWLP group for each outcome.

Exploratory Analyses. Additional 2 x 2 RM-ANOVA's for each outcome variable, including depressive and anxious symptoms, rumination, maladaptive eating, self-esteem, cognitive flexibility and self-judgement will be examined.

Finally, significant changes in weight bias and IWB will be examined as predictors of weight loss and psychological outcomes.

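### Does the plan need to name which ANOVA term decides whether each group was successful?

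*Combined protocol and SAP*

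**What the plan says.** The paragraph on Hypotheses One and Two in the Statistical Analysis Plan gives the 2 × 2 repeated measures ANOVA two tasks. The first is to judge "whether the BWLP only and Third-Wave + BWLP groups were successful with lowering weight, IWB, and weight bias" (healthy eating and physical activity are added to the list). The second is to judge "whether there are differences between the BWLP only group with the Third-Wave + BWLP group for each outcome". It does not assign a main effect, interaction, within-arm contrast or threshold to either task. The two hypotheses themselves are not worded in the document.

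The sample-size text under Participants says that "a sample size of 40 will be required to detect a medium effect size" in such an ANOVA, and again names no term. Planned enrolment is 70, with 35 per arm.

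Under Interventions, every participant receives the weight loss programme. Under Procedure, "only one group will be administered a third-wave, ACT and self-compassion-based IWB intervention", while in the shared sessions "group leaders will look for opportunities to incorporate weight bias reduction strategies throughout the DPP when possible". The Measures section states that "All measures will be completed at baseline and post-intervention online". The Exploratory Analyses paragraph adds that "significant changes in weight bias and IWB will be examined as predictors of weight loss and psychological outcomes".

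**The concern.** A 2 × 2 repeated measures ANOVA has three omnibus terms. Group compares the arms averaged over both time points. Time by group compares the arms' changes. Time tests change from baseline, but averaged over the arms. The first question is about each named group, and no omnibus term answers that.

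If the time effect were used by default, a significant time effect with a non-significant interaction could be reported as both programmes having worked when one arm barely moved. Internalized weight bias and weight bias are the outcomes most exposed, because only one arm gets the dedicated sessions. The Internalized Weight Bias section also recalls an earlier trial with no change on the WBIS at 12 weeks.

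Two further worries follow. With no untreated arm, pre-post change cannot be credited to the weight loss programme. And the exploratory analysis carries forward changes called significant without saying which test makes them so.

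**Working it through.** **Inputs from the document.** Two arms, two time points, equal allocation; 40 required and 70 planned.

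**Assumptions (not in the document).** Two-sided 5% level; a medium effect taken as f = 0.25; change scores with SD 1 and a pooled variance on N − 2 df. True changes d_A and d_B are in SDs of change. Results are shown over a range.

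**1. The plan's own figure.** For time and for time by group, the noncentrality is λ = f²·N·m/(1 − ρ), with m = 2 time points and ρ the baseline-to-post correlation.
- ρ = 0.4, N = 40: λ = 0.0625 × 40 × 2/0.6 = 8.33, power 0.80.
- ρ = 0.5, N = 40: λ = 10, power 0.87. At this ρ, 34 participants suffice for 0.80.
- The group main effect would need 66 to 116 participants for 0.80 power (ρ from 0 to 0.8).

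So 40 is reachable for the time or interaction term and does not fit the group term. Since ρ, power and level are not stated, the figure can be neither confirmed nor faulted.

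**2. How often the misleading pattern arises.** Noncentrality of the time test is ((d_A + d_B)/2)·√N, and of the interaction ((d_B − d_A)/2)·√N. The table gives the probability that time is significant in the improving direction and the interaction is not.

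| d_A | d_B | N = 40 | N = 70 |
|---|---|---|---|
| 0 | 0.5 | 21.7% | 24.4% |
| 0 | 0.6 | 24.0% | 20.8% |
| 0 | 0.8 | 20.6% | 8.1% |
| 0 | 1.0 | 11.1% | 1.5% |
| 0.1 | 0.5 | 34.3% | 42.9% |
| 0.1 | 1.0 | 19.0% | 4.0% |

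Simulation reproduces these rates to within about 0.3 percentage points. In the rows with d_A = 0.1, saying that both arms changed is true; the pooled test only hides how small one change is.

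The sizing in step 1 gives some scale. With f = 0.25 on the interaction and ρ = 0.5, (d/2)² × 40 = 10, so d = 1.0. If that is what the plan was sized for, the 1.0 SD row is the relevant one.

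**3. What separate per-arm verdicts would do.** Let both arms truly change by 0.5 SD.
- Pooled time effect: power 87% at N = 40 and 98.5% at N = 70.
- A given arm's 95% interval excludes zero (noncentral t, n = N/2, noncentrality 0.5·√n): 56.4% and 82.0%.
- Both arms' intervals exclude zero: 31.9% and 67.2%.
- Exactly one does: 2 × (56.4 − 31.9) = 49% and 2 × (82.0 − 67.2) = 30%.

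Interval half-width is t(0.975, n − 1)/√n per arm: 0.47 SD at n = 20 and 0.34 SD at n = 35. Pooled over arms it is 0.32 and 0.24.

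**4. Reading the text.** The plan asks first about change and then about difference between groups. In a two-time-point design these correspond to time and to time by group. Both tests come out of the model as specified, and arm-level means come with it.

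**The case for a change.** The strongest case for a change is that the question is put about each group, the specified model does not answer it at omnibus level, and a line of text settling the rule would cost almost nothing. It would also stop the choice between pooled and per-arm claims from being made after the results are seen. That reasoning is sound as far as it goes: the term is not named, and the rates in the table are correct for the assumed effects.

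Less stands on consequences. The row with an inert arm needs a group that gains nothing, although both arms attend the diabetes prevention sessions and leaders work weight bias strategies into them. For weight, eating and activity that is improbable; for internalized weight bias it is possible. The earlier trial is mixed evidence, since the same sentence reports differences on the WSSQ, and this trial uses both scales.

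The missing untreated arm limits what pre-post change can mean, but the plan does not claim an effect against no treatment, and the add-on design is sound for the third-wave component. Per-arm intervals are just as uncontrolled, so on attribution the gain would be labelling only.

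Screening on the WBIS at 4 or higher could add regression to the mean if the screening score doubled as baseline. The Measures section, however, has all scales completed at baseline.

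The predictor rule is loose, but it belongs to an exploratory analysis and does not touch the randomised comparison.

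**Conclusion.** No change to the plan follows. This is an unwritten detail that analysts fill sensibly: time by group tests the added third-wave component, and arm-level changes are described as uncontrolled pre-post change. The randomised contrast, the data collected and the sample size are unaffected.

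The risk is one of reporting. It amounts to 22% to 24% of trials if one arm is wholly inert and the other changes by 0.5 SD, and 1.5% at 1.0 SD with 70 participants. Replacing the pooled reading with a significance verdict for each arm would not clearly improve matters. When both arms truly change by 0.5 SD, it splits them in about 49% of trials at 40 participants and 30% at 70, which invites the opposite error of saying that only one programme worked.

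These figures rest on assumed effect sizes, equal variances and equal arms. Because Hypotheses One and Two are not worded in the document, the intended meaning of success cannot be checked; that limits confidence in either direction.

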Internalized Weight Bias. IWB will be measured by both the Weight Bias Internalization Scale (WBIS; Durso & Latner, 2008; Appendix C) and Weight Self-Stigma Questionnaire (WSSQ; Lillis et al., 2010; Appendix D). Both measures were chosen for several reasons. First, Pearl, Wadden, Bach, Gruber, et al. (2020) found participant differences on the WSSQ at a 12-week assessment of IWB, but did not see a change on the WBIS. Second, while both are commonly used throughout IWB literature, some IWB interventions only used the WSSQ (Lillis et al., 2009; Palmeira, Cunha, & Pinto-Gouveia, 2017) and some only used the WBIS (Pearl, Hopkins, et al., 2018). Because this study aims to build upon previous approaches to lowering IWB, both scales will be considered to increase generalizability to all relevant past findings. Both scales have been found to be predictive of IWB, have comparable reliability convergent validity, and are strongly correlated (Hübner et al., 2016).

In 2008, Durso and Latner developed the WBIS, which was an 11-item scale used to assess IWB among populations with overweight and obesity using a 7-point Likert scale. According to the authors, the scale was created using existing literature on antifat attitudes and similar questionnaires on internalized homophobia. The WBIS uses questions that assess the extent to which an individual accepts or rejects their weight (e.g., “Because I’m overweight, I don’t feel like my true self.”), the desire to change their weight (e.g., “I wish I could drastically change my weight.”), or how their weight influences their self-perception or mood (“I am less attractive than most other people because of my weight.”). The authors report excellent

internal consistency ($\alpha = 0.90$) for the scale. In addition, they reported good validity as the WBIS was moderately correlated with measures of antifat attitudes, self-esteem, and body image concerns when controlling for BMI.

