The EDDS – DSM 5 Version is 22-item a questionnaire designed to assess symptoms of anorexia nervosa, bulimia nervosa, and binge-eating disorder per DSM-5 criteria. The questions vary in terms of format, using 6-point Likert ratings from “Not at all” to “Extremely,” dichotomous items and asking about frequency of diagnostically relevant behavior over a set period of time (i.e., days per week for over X amount of months). The EDDS has demonstrated reliability for each disorder, including anorexia (kappa = .95), bulimia (kappa = .71), and binge-eating disorder (kappa = .75). Content validity was established through review by 14 eating disorder experts.

Mental Health. Mental health will be assessed using the 21-item Depression Anxiety and Stress Scale (DASS-21; Appendix K), as it can assess clinically relevant depressive symptoms,

anxious symptoms, and stress all within 21-items (Lovibond & Lovibond, 1995). Participants rate to which extent each symptom applied to them within the past week, from 1 (did not apply to me at all) and 4 (applied to me very much, or most of the time). Each scale has demonstrated good reliability, with α 's = .91, .80, and .84 for Depression, Anxiety, and Stress, respectively (Sinclair et al., 2011). The scale has also demonstrated constructive validity within a large, non-clinical sample (Henry & Crawford, 2005).

In addition, rumination will specifically be examined using the Ruminative Response Scale-Short Form (RRS-SF; Treynor et al., 2003; Appendix L). Wang et al. (2017) found IWB to be moderately and significantly correlated with brooding rumination ($r = .56$) among a sample of individuals with obesity and binge eating disorder. Thus, rumination may be relevant and of interest to aim three as to how IWB may affect weight loss efforts. The RRS-SF includes nine items with two subscales; brooding and reflection. The form utilizes a 4-point Likert scale ranging from 1 ("almost never") to 4 ("almost always") for various aspects of rumination. The two subscales have shown to have acceptable reliability in a clinical and nonclinical samples, with α 's = .79 and .75 for brooding and reflection, respectively. Construct validity was also demonstrated with moderate correlations to the subscales of the DASS-21 (Ruiz et al., 2017).

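### The exploratory predictor analysis picks its predictors by whether their mean change was significant, and specifies no model, so it can miss a real association or let an arm effect pass as one

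*Combined protocol and SAP*

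**What the plan says.** The Exploratory Analyses part of the Statistical Analysis Plan ends with one sentence on prediction: "significant changes in weight bias and IWB will be examined as predictors of weight loss and psychological outcomes". It does not define significance, name a model or covariates, mention arm, or say what happens to a scale whose change is not significant.

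Five other places bear on it:

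- **Statistical Analysis Plan, Hypothesis One and Hypothesis Two.** The 2 x 2 time-by-group ANOVAs that would supply the significance results also test "whether there are differences between the BWLP only group with the Third-Wave + BWLP group for each outcome". Weight, IWB and weight bias are among those outcomes.
- **Statistical Analysis Plan, opening paragraph.** After the baseline demographic comparison, "any potential group differences will be included as a covariate in analyses". This concerns characteristics on which the groups differ and does not place arm in the predictor model.
- **Procedure.** "only one group will be administered a third-wave, ACT and self-compassion-based IWB intervention", while leaders in both groups may work weight bias strategies into the shared weight loss sessions.
- **Measures, Internalized Weight Bias.** Two IWB scales are used, partly because an earlier trial "found participant differences on the WSSQ at a 12-week assessment of IWB, but did not see a change on the WBIS".
- **Measures, Mental Health.** In passing: "rumination may be relevant and of interest to aim three as to how IWB may affect weight loss efforts".

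**The concern.** Two separate questions are tied together. Whether a scale's mean moved is a question about the group. Whether participants whose score moved further also lost more weight is a question about individuals. The mean change can be zero while the individual slope is steep, so screening on the first discards tests of the second without making the remaining tests any better. The protocol's own account of an earlier trial, with a difference on the WSSQ and no change on the WBIS, shows that one of the two chosen IWB scales could fail such a screen.

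The second issue is that arm could be a common cause. Only one group receives the IWB sessions. If arm also affects weight, a regression that pools the groups can show IWB change predicting weight loss when no such relation exists within either group. The unspecified model leaves that possible.

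What is at stake is the interpretation of an exploratory result on how IWB relates to weight loss and psychological outcomes.

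**Working it through.** **Inputs.** From Participants: 40 required, 70 enrolled, 35 per group. I use 40 and 70 as the lower and upper analysed sample sizes. Not stated in the documents and assumed here: two-sided alpha 0.05, true correlation r = 0.4 between predictor change and outcome change, standardised mean change dz = 0.2 to 0.5, and arm shifts of 0.2 to 1.0 SD on the change scores.

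**The plan's own figure.** The predictor analysis has no sample size of its own. The stated 40 is for the 2 x 2 ANOVA, without alpha, power or pre-post correlation, so it cannot be confirmed from stated inputs. Taking a medium effect as f = 0.25, the interaction noncentrality is f² x N x 2/(1 - rho). With N = 40 and rho = 0.4 this is 0.0625 x 40 x 2/0.6 = 8.33, which gives power 0.80. The figure of 40 is attainable and is not shown to be wrong.

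**Step 1: how often the screen opens.** Model it as a one-sample t-test on mean change, with noncentrality dz x √N. For dz = 0.2 and N = 40 this is 0.2 x 6.325 = 1.26 on 39 df, giving 23.5%.

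**Step 2: power without the screen.** By Fisher's z, atanh(0.4) x √(N - 3) = 0.4236 x 6.083 = 2.58 at N = 40, giving 73%. At N = 70 it is 0.4236 x 8.185 = 3.47, giving 93%.

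**Step 3: combine.** Under bivariate normality the sample mean and sample correlation are independent, so power with the screen is the product.

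| dz | Screen opens, N=40 | Power with screen, N=40 | Screen opens, N=70 | Power with screen, N=70 |
|---|---|---|---|---|
| 0.2 | 24% | 17% | 38% | 35% |
| 0.3 | 46% | 33% | 70% | 65% |
| 0.5 | 87% | 64% | 98% | 92% |

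**Step 4: a screen closer to the ANOVA.** In simulation (20,000 trials per scenario) a scale passes if either the time or the interaction effect is significant. With zero mean change in both arms, it goes untested in about 90% of trials. With a mean change and an arm difference of 0.2 SD each, it goes untested in 70% (N = 40) or 55% (N = 70). With 0.5 SD each, the figures are 9% and 1%. If only the interaction counts, the 0.5 SD case goes untested in 67% and 46%. The undefined effect therefore matters in itself.

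**Step 5: pooling over arm.** With equal arms, shifts d1 and d2 and no within-arm association, the pooled correlation is about 0.25 x d1 x d2/√[(1 + 0.25 d1²)(1 + 0.25 d2²)]. For d1 = d2 = 1.0 this is 0.25/1.25 = 0.20. For 0.8 it is 0.16/1.16 = 0.14, and for 0.5 it is 0.0625/1.0625 = 0.06. Simulated false-positive rates:

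| Arm shift on IWB / weight (SD) | Pooled, N=40 | Pooled, N=70 | With arm |
|---|---|---|---|
| 0.5 / 0.5 | 6% | 8% | about 5% |
| 1.0 / 0.2-0.3 | 6-7% | 7-8% | about 5% |
| 0.8 / 0.8 | 14% | 21% | about 5% |
| 1.0 / 1.0 | 24% | 39% | about 5% |

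Among trials that pass the screen at 1.0 / 1.0, the pooled rates are 26% and 40%.

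**Where 1.0 SD comes from.** Equating the interaction noncentrality with N x d²/4 gives d = √[8 x 0.0625/(1 - rho)] = √[0.5/(1 - rho)]. This is 0.71, 0.91 and 1.0 at rho = 0, 0.4 and 0.5. The planned medium effect can therefore correspond to a shift of that size on one variable. It does not follow that it applies to both variables at once.

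**The case against.** The strongest reply is that the sentence is brief and not necessarily faulty. It never says that non-significant changes will be left out, and it never says that arm will be omitted. A reader might infer that the plan excludes arm. It does not: it gives no model at all, so the omission is silence. That stands. What remains is that the wording permits the pooled model, and that it names significant changes as the predictors, for which screening is the natural meaning.

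A second reply is that the screen may rarely bind. Participants are selected at a cutoff of 4 or higher on internalized weight bias, which invites regression to the mean, and both groups may receive some weight bias strategies. Both make a mean change in IWB plausible, and at dz = 0.5 the loss is small with 70 participants. This stands for IWB under a time-effect screen. It is weaker for the SSI-B and UMB-FAT. It does not help under an interaction-only screen, because strategies delivered in both groups could narrow the difference between them.

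A third reply is that the high false-positive rates need large arm effects on weight as well as IWB. A reader might infer that the plan expects arm to move both. The documents do not support that: they ask whether the groups differ, and both groups receive the same weight loss programme. With a small effect on weight, the inflation is 1 to 3 percentage points above nominal.

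**Conclusion.** The point holds as a weakness of an exploratory analysis. The selection rule bears no relation to the question asked, and its cost runs from slight (93% to 92% at dz = 0.5, N = 70) to severe (73% to 17% at dz = 0.2, N = 40), given r = 0.4 and a screen on mean change. The unspecified model adds a risk of confounding by arm. That risk is small (6-8% false positives) under modest or one-sided arm effects, and substantial (14-24% at N = 40, 21-39% at N = 70) only when arm shifts both variables by 0.8-1.0 SD.

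Two further readings go beyond the text. One is that this is the only analysis serving aim three: the document does not list its aims and mentions aim three only in passing. The other is that participants will be split into changed and unchanged: nothing in the plan describes such a split.

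Hypotheses One and Two are not affected.

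**What to change.** Replace the closing sentence of the Exploratory Analyses with:

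> Change in WBIS, WSSQ, SSI-B and UMB-FAT will each be entered as a continuous predictor of weight change and psychological outcomes, whether or not the mean change is significant, in a regression that includes treatment arm. Because predictor and outcome changes are measured over the same interval, results are reported as exploratory associations without direction and without multiplicity adjustment.

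Adjustment for baseline values is optional; neither problem above requires it. The cost is one or more extra covariates and a larger number of exploratory tests, which the last sentence of the replacement text discloses. No new data or visits are needed, and the models run in the SPSS already planned.
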